4.7 Criteria for Removal of Patient from Protocol Participation

- a. Patient completes 12 months of study participation.
- b. Patient does not receive at least one cycle of chemotherapy within the first 90 days after registration.
- c. The patient may withdraw from the study at any time for any reason. (Research staff should only submit the S1417CD Off Protocol Notice if the patient refuses both direct and indirect follow-up on the study. If the patient allows for indirect follow-up or is refusing to complete any further patient forms but will allow the site to follow them directly, do not submit the S1417CD Off Protocol Notice and continue to submit the site-completed forms at the time points required in Section 9.4b.)
- d. Patient death.

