3.1 Disease Related Criteria

a. Patients must have newly diagnosed metastatic colon or rectal cancer (mCRC) (de novo metastatic diagnosis) or metastatic recurrence after prior treatment for Stage I-III disease and be ≤ 120 days after diagnosis at time of registration.

b. Systemic chemotherapy and/or systemic biologic therapy must be planned to be administered ≤ 30 days *after* registration OR must have been initiated ≤ 60 days *prior* to registration. Patients who are planning palliative or hospice care only (no chemotherapy or biologic therapy) are not eligible.

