4.9 Follow-up Period

No further follow-up will be required once the patient completes 12 months of study participation or if the patient discontinues study participation as defined in Sections 4.7b, 4.7c and 4.7d prior to 12 months of participation and the S1417CD Off Protocol Notice is submitted.

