6.0 CRITERIA FOR EVALUATION AND ENDPOINT ANALYSIS

- 6.1 Primary Endpoint
 - a. Major Financial Hardship: Defined as one or more of the following during the 12 month study period: debt accumulation of any amount, selling or refinancing home, ≥ 20% income decline, borrowing money of any amount from family/friends.
- 6.2 Secondary Endpoints
 - a. Treatment Non-Adherence: Defined as refusing treatment or skipping doses due to cost concerns (e.g., lack of coverage, high co-payment requirement)

- b. Health-related Quality of Life (HRQOL): As measured by the EORTC Quality of Life Questionnaire C30 (QLQ-C30) v. 3.0. (14) This is a well-validated questionnaire which includes 30 items assessing global quality-of-life, functioning in five domains (physical, role, cognitive, emotional social) and several items assessing specific symptoms (e.g. fatigue, trouble sleeping, pain). Importantly, the QLQ-C30 does include one item assessing the impact of medical treatment on finances. Questionnaire responses will be transformed into a linear score (0 to 100) using the EORTC scoring manual.
- c. Out-of-Pocket Expenses: Defined as total out-of-pocket direct medical (e.g., prescriptions, physician visits, deductibles) and non-medical (transportation, meals) expenses in the 3 months prior to each study visit.
- d. Credit History (TransUnion): Credit reports are obtained at baseline, 6 months, and when the patient goes off protocol and measure the following: non-mortgage amounts past due on credit cards and bankcards; non-mortgage credit card and bankcard balances; bankruptcies, liens, collections or repossessions.

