6.4 Questionnaires

The majority of items in the final financial impact assessment tool were adapted from the a questionnaire used in our previous work that was successfully administered to a population-based sample of patients with stage III colon cancer in the Seattle/Puget Sound region. (15) Several questions were also adapted from the Medical Expenditures Panel Survey (MEPS), a large-scale survey of households, employers, and medical providers on the cost and use of health care in the United States and the University of Michigan's Health and Retirement Study (HRS), a longitudinal panel survey of older adults. (16) The EORTC Quality of Life Questionnaire (QLQ C-30), an existing, validated quality of life instrument, will also be used to assess HRQOL. (17) Questions measuring caregivers' stress and anxiety related to cancer treatment expenses were adapted from a questionnaire used in the Family and Cancer Therapy Selection (FACTS) Study conducted at the Fred Hutchinson Cancer Research Center as well as the Caregiver Strain Index, an existing validated survey of cancer caregiver burden. Additional questions were obtained from a survey-based study of caregivers performed by Evercare, in collaboration with the National Alliance for Caregiving, entitled "Family Caregivers: What they Spend, What they Sacrifice." (18) The final questionnaires focus on different aspects of patients' or caregivers' financial experience:

BASELINE QUESTIONNAIRE: Baseline patient financial, employment, and insurance characteristics – education level, annual income, preexisting debt, total assets (including retirement and savings), baseline employment status.

FINANCIAL/EMPLOYMENT IMPACT QUESTIONNAIRE: **Treatment-related financial or employment changes** – accumulation of debt, depletion of assets, inability to pay other bills, changes in income, job loss, borrowing money, selling home.

INSURANCE IMPACT QUESTIONNAIRE: Treatment-related insurance issues and out-of-pocket expenses – insurance coverage denials, high copayments, changes in premiums, treatment non-adherence, all treatment-related out-of-pocket expenses.

QUALITY OF LIFE QUESTIONNAIRE: Health-related quality of life – EORTC Quality of Life Questionnaire (QLQ C-30)

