8.0 REGISTRATION GUIDELINES

8.1 Registration Timing

Registration must be within 120 days after diagnosis of metastatic colorectal cancer. Treatment must start \leq 30 days after registration or must have been initiated \leq 60 days prior to registration.

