9.4 Data Submission Timeline

a. WITHIN 7 DAYS AFTER REGISTRATION:

Submit the following site completed form:

S1417CD Onstudy Form

S1417CD Cover Sheet for Patient and Caregiver-Completed Questionnaires

Submit the following patient-completed questionnaires:

S1417CD Baseline Questionnaire

S1417CD Quality Of Life Questionnaire

S1417CD Treatment Perceptions Questionnaire

Submit the following caregiver-completed questionnaire:

S1417CD Caregiver Questionnaire (if caregiver consented)

- b. WITHIN 7 DAYS AFTER PATIENT COMPLETES QUESTIONNAIRE* AT MONTHS 3, 6, 9 AND 12 STUDY TIMEPOINTS:
 - * A +/- 21-day window is permitted for administration of patient and caregiver follow-up questionnaires. See Sections 4.3b and 10.2b.

Submit the following site-completed forms:

S1417CD Follow-Up Patient Status and Disease Characteristics

S1417CD Cover Sheet for Patient and Caregiver-Completed Questionnaires

NOTE: If a patient cannot or refuses to complete forms at a specific time point, the site-completed forms must still be submitted. Refer to $\frac{\text{Sections 4.7c}}{\text{Sections 4.7c}}$ and $\frac{\text{4.8}}{\text{Sections 4.7c}}$.

Submit the following patient-completed forms:

S1417CD Financial/Employment Impact Questionnaire

S1417CD Insurance Impact Questionnaire

\$1417CD Quality Of Life Questionnaire

S1417CD Treatment Perceptions Questionnaire

Submit the following caregiver-completed form:

S1417CD Caregiver Questionnaire (at months 6 and 12 only, if caregiver consented)

c. WITHIN 7 DAYS AFTER PATIENT DISCONTINUES PROTOCOL PARTICIPATION:

Submit the following patient-completed form:

S1417CD Off Protocol Notice

NOTE: The **S1417CD** Off Protocol Notice is submitted to reflect the patient's participation status only. If the consented caregiver discontinues study

participation prior to the patient's completion of 12 months of study participation, refer to Section 10.3 for instructions for reporting caregiver discontinuation on the S1417CD Cover Sheet for Patient and Caregiver-Completed Questionnaires.

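### Removal rule 4.7b counts only chemotherapy, while eligibility rule 3.1b also admits patients on biologic therapy alone; the wording should be reconciled (low severity).

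*Combined protocol and SAP*

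**What the plan says.** **Entry.** Section 3.1b reads "Systemic chemotherapy and/or systemic biologic therapy must be planned to be administered" within 30 days after registration, or else begun no more than 60 days before it. The same section states that patients planning "palliative or hospice care only (no chemotherapy or biologic therapy) are not eligible". The schema repeats the treatment requirement. Section 8.1 uses a neutral term, "Treatment must start", with the same time limits.

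**Removal.** Section 4.7b gives as a criterion for removal: "Patient does not receive at least one cycle of chemotherapy within the first 90 days after registration". Biologic therapy is not mentioned.

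**Consequence.** Section 4.9 states "No further follow-up will be required once the patient completes 12 months of study participation or if the patient discontinues study participation" under 4.7b, 4.7c or 4.7d before 12 months and the Off Protocol Notice is submitted. Section 9.4c sets the notice deadline: "WITHIN 7 DAYS AFTER PATIENT DISCONTINUES PROTOCOL" participation. Section 4.8 requires the reason for discontinuation to be recorded on that notice. Section 7.1 censors dropouts for reasons other than death.

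**Non-adherence.** Section 6.2a describes this endpoint as "Defined as refusing treatment or skipping doses due to cost concerns". In Section 6.4 it is covered by the Insurance Impact Questionnaire, whose topics include "insurance coverage denials, high copayments, changes in premiums, treatment non-adherence". The study calendar schedules that form, and the Financial/Employment Impact Questionnaire, at months 3, 6, 9 and 12 but not at baseline.

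**The concern.** The entry rule and the removal rule use different definitions of being treated. A patient can satisfy the first, receive exactly the treatment that made them eligible, and still meet the second. The primary objective in Section 1.1 concerns hardship over 12 months in patients treated at NCORP sites, so such a patient belongs to the target population. Losing the patient at about month 3 discards information that the study set out to collect.

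It also sits oddly with the rest of Section 4. Under 4.7c and 4.8, a patient who declines every questionnaire stays on protocol as long as some follow-up is allowed. A willing patient on biologic therapy alone would not.

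There is a secondary matter of timing. A patient who refuses all chemotherapy because of cost, and so has no cycle after registration, meets the non-adherence endpoint and the removal criterion together. The 90-day limit falls inside the window for the first questionnaire that asks about non-adherence.

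**Working it through.** The plan states no figure on this point that needs to be reproduced. The check compares the sections and then counts days.

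**Step 1: does 3.1b treat the two therapies as separate?** Yes. It joins them with and/or, and its exclusion applies only to patients with neither. Biologic therapy alone therefore qualifies.

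**Step 2: could the word chemotherapy in 4.7b cover biologic therapy?** Nothing in the documents defines it that way, and 3.1b uses the two terms side by side as different things. The text does not support the broader reading, although loose drafting is a plausible explanation.

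**Step 3: follow one patient through the rules.**

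| Rule | Patient on biologic therapy alone |
|---|---|
| 3.1b, eligibility | Eligible |
| 8.1, start of treatment | Met |
| 4.7b, removal | Criterion met once day 90 passes without a chemotherapy cycle |
| 4.9, follow-up | None required after the notice |
| 7.1, primary analysis | Censored, as a dropout not due to death |

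The last row is an inference: the examples of dropout in 7.1 are transfer of care and withdrawal of consent, and it does not name removal under 4.7b. It is, however, the only rule given for leaving the study alive.

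**Step 4: what is lost?** Hardship is asked at four follow-up times: months 3, 6, 9 and 12. Removal just after day 90 leaves at most the first, so three of the four assessments and about 12 − 3 = 9 months of observation are lost for that patient.

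**Step 5: timing for a patient who refuses all chemotherapy over cost.**

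- Month-3 target: three calendar months are 90 to 92 days; take 91.
- Window (Section 4.3b, ± 21 days): 91 − 21 = 70 to 91 + 21 = 112, which is 112 − 70 + 1 = 43 days.
- Notice deadline, if removal takes effect when day 90 passes: 90 + 7 = day 97.
- Split of the window: days 70 to 90 (21 days) precede removal, days 91 to 97 (7 days) are the filing period, and days 98 to 112 (15 days) follow the deadline. The sum is 21 + 7 + 15 = 43.

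A form completed on its target date is in hand about 97 − 91 = 6 days before the deadline. A form completed late in the window may come after the patient has left the protocol. Section 9.4c lists only the notice at discontinuation, not a final Insurance Impact form.

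**The case against.** The strongest reply is that this is a drafting slip with no demonstrated consequence. The conflict arises only for a patient who receives biologic therapy and not a single chemotherapy cycle in the 90 days after registration; one cycle in that period is enough to avoid removal. The documents do not say how many such patients are expected, or that any are. Sites may also read the rule in the sense of 3.1b. All of this stands and limits the weight of the point. It does not remove the contradiction, because 4.7 is the list that sites apply and different sites may read it differently.

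A reader might go further and infer that patients who refuse treatment over cost are systematically missed. The documents do not support that. The month-3 target falls before the notice deadline. Section 4.9 says that follow-up is not required, which does not forbid a month-3 form. Section 4.3d allows a phone interview. Section 4.8 puts the reason for removal on the notice, so a cost refusal may be recorded there; the content of that form is not in the documents, and nothing says that it would count toward 6.2a. The 15 of 43 window days after the deadline are not a probability of loss, since completion dates need not be spread evenly over the window. Patients who refuse or skip doses after one cycle following registration are not touched by 4.7b at all.

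Section 4.6 also obtains a credit report when a patient goes off protocol early. Some financial information is therefore taken at removal, though it does not replace the questionnaire-based primary endpoint.

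**Conclusion.** The inconsistency between 3.1b and 4.7b is real as written, and its severity is low. Applied literally, 4.7b together with 4.9 ends follow-up at about month 3 for patients who are eligible and under treatment. This rests on two readings: that chemotherapy in 4.7b means what it means in 3.1b, and that patients removed under 4.7b fall under the censoring rule of 7.1.

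The number affected cannot be derived from the documents. A reader might infer that the 12-month hardship incidence is materially biased. That is not shown: any estimate would need the share of patients removed and their hardship risk, neither of which is given, and the direction of the effect would depend on that risk. No sample size, power or alpha figure changes.

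The possible loss of month-3 non-adherence data is secondary. It can happen, but it need not.

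**What to change.** **Main change.** Reconcile the treatment wording of 4.7b with 3.1b and 8.1, so that patients who are eligible and treated are not removed from follow-up. Which wording is right is for the sponsor. The cost is a short amendment with no new data collection.

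**Optional.** State in 4.7b and 4.9 that, for patients who meet 4.7b, the existing month-3 Financial/Employment Impact and Insurance Impact forms are collected before the Off Protocol Notice is filed, using the phone interview in 4.3d where the patient does not attend clinic. The downside is one existing set of questionnaires, 30 to 60 minutes by Section 4.3a, from a probably small group. Whether patients who are never treated should stay on the later schedule is a separate choice for the sponsor and is not part of this request.

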4.8 Discontinuation of Study Participation

All reasons for discontinuation of study participation as defined in Section 4.7, including patient death, must be documented on the S1417CD Off Protocol Notice and submitted per Section 9.4c.

NOTE: If a patient cannot or refuses to complete the patient questionnaires for a study time point, this is not a criterion for discontinuation of protocol participation. Do not submit the **S1417CD** Off Protocol Notice. Submit the site-completed forms for the time point per Section 9.4b, the **S1417CD** Cover Sheet for Patient- and Caregiver-Completed Questionnaires documenting the reason the questionnaires were not completed at the time point and the **S1417CD** Follow-up Patient Status and Disease Characteristics form at the time point. Administer questionnaires to the patient at the next study time point. See also Section 4.7c for additional follow-up and forms management information.

4.9 Follow-up Period

No further follow-up will be required once the patient completes 12 months of study participation or if the patient discontinues study participation as defined in Sections 4.7b, 4.7c and 4.7d prior to 12 months of participation and the S1417CD Off Protocol Notice is submitted.

5.0 STUDY CALENDAR

| REQUIRED | Prestudy/ Baseline | Month 3 | Month 6 | Month 9 | Month 12 |
|---|-----------------------|------------|------------|------------|-------------|
| PATIENT QUESTIONNAIRES | | | | | |
| S1417CD Baseline Questionnaire | Х | | | | |
| S1417CD Financial/Employment Impact Questionnaire | | Х | Х | Х | Х |
| S1417CD Insurance Impact Questionnaire | | Х | Х | Х | Х |
| S1417CD Quality Of Life Questionnaire | Х | Х | Х | Х | Х |
| S1417CD Treatment Perceptions Questionnaire | Х | Х | Х | Х | Х |
| CAREGIVER QUESTIONNAIRE | | | | | |
| S1417CD Caregiver Questionnaire √ | Х | | Х | | Х |
| SITE COMPLETED FORMS | | | | | |
| S1417CD Registration Worksheet (Not submitted) | Х | | | | |
| S1417CD Onstudy Form | Х | | | | |
| S1417CD Follow-Up Patient Status and Disease Characteristics | | Х | Х | Х | Х |
| S1417CD Cover Sheet for Patient- and Caregiver- Completed Questionnaires | Х | Х | Х | Х | Х |
| S1417CD Off Protocol Notice | | | | | ΧΩ |

NOTE: Forms are found on the protocol abstract page on the SWOG website (www.swog.org) or CTSU member website (https://www.ctsu.org). Forms submission guidelines are found in Section 9.0.

- √ For consenting caregivers (optional). See Section 10.0 for administration guidelines.
- Ω If patient discontinues study participation earlier than 12 months, submit the **S1417CD** Off Protocol Notice per Section 4.8.

6.0 CRITERIA FOR EVALUATION AND ENDPOINT ANALYSIS

- 6.1 Primary Endpoint
 - a. Major Financial Hardship: Defined as one or more of the following during the 12 month study period: debt accumulation of any amount, selling or refinancing home, ≥ 20% income decline, borrowing money of any amount from family/friends.
- 6.2 Secondary Endpoints
 - a. Treatment Non-Adherence: Defined as refusing treatment or skipping doses due to cost concerns (e.g., lack of coverage, high co-payment requirement)

- b. Health-related Quality of Life (HRQOL): As measured by the EORTC Quality of Life Questionnaire C30 (QLQ-C30) v. 3.0. (14) This is a well-validated questionnaire which includes 30 items assessing global quality-of-life, functioning in five domains (physical, role, cognitive, emotional social) and several items assessing specific symptoms (e.g. fatigue, trouble sleeping, pain). Importantly, the QLQ-C30 does include one item assessing the impact of medical treatment on finances. Questionnaire responses will be transformed into a linear score (0 to 100) using the EORTC scoring manual.
- c. Out-of-Pocket Expenses: Defined as total out-of-pocket direct medical (e.g., prescriptions, physician visits, deductibles) and non-medical (transportation, meals) expenses in the 3 months prior to each study visit.
- d. Credit History (TransUnion): Credit reports are obtained at baseline, 6 months, and when the patient goes off protocol and measure the following: non-mortgage amounts past due on credit cards and bankcards; non-mortgage credit card and bankcard balances; bankruptcies, liens, collections or repossessions.

6.3 Definition of Primary Caregiver

a. Primary caregiver is defined as a family member or friend who provides the greatest degree of emotional, physical, logistical, and/or financial support in navigating cancer treatment

6.4 Questionnaires

The majority of items in the final financial impact assessment tool were adapted from the a questionnaire used in our previous work that was successfully administered to a population-based sample of patients with stage III colon cancer in the Seattle/Puget Sound region. (15) Several questions were also adapted from the Medical Expenditures Panel Survey (MEPS), a large-scale survey of households, employers, and medical providers on the cost and use of health care in the United States and the University of Michigan's Health and Retirement Study (HRS), a longitudinal panel survey of older adults. (16) The EORTC Quality of Life Questionnaire (QLQ C-30), an existing, validated quality of life instrument, will also be used to assess HRQOL. (17) Questions measuring caregivers' stress and anxiety related to cancer treatment expenses were adapted from a questionnaire used in the Family and Cancer Therapy Selection (FACTS) Study conducted at the Fred Hutchinson Cancer Research Center as well as the Caregiver Strain Index, an existing validated survey of cancer caregiver burden. Additional questions were obtained from a survey-based study of caregivers performed by Evercare, in collaboration with the National Alliance for Caregiving, entitled "Family Caregivers: What they Spend, What they Sacrifice." (18) The final questionnaires focus on different aspects of patients' or caregivers' financial experience:

BASELINE QUESTIONNAIRE: Baseline patient financial, employment, and insurance characteristics – education level, annual income, preexisting debt, total assets (including retirement and savings), baseline employment status.

FINANCIAL/EMPLOYMENT IMPACT QUESTIONNAIRE: **Treatment-related financial or employment changes** – accumulation of debt, depletion of assets, inability to pay other bills, changes in income, job loss, borrowing money, selling home.

INSURANCE IMPACT QUESTIONNAIRE: Treatment-related insurance issues and out-of-pocket expenses – insurance coverage denials, high copayments, changes in premiums, treatment non-adherence, all treatment-related out-of-pocket expenses.

QUALITY OF LIFE QUESTIONNAIRE: Health-related quality of life – EORTC Quality of Life Questionnaire (QLQ C-30)

TREATMENT PERCEPTIONS QUESTIONNAIRE: Subjective financial burden assessment – which includes questions assessing stress, anxiety, and guilt related to cancer treatment costs as well as prioritization of treatment costs in the list of disease-related concerns.

CAREGIVER QUESTIONNAIRE: (Consented caregiver only.) Assessment of financial changes made to accommodate patient's cancer treatment expenses and subjective caregiver burden assessment (adapted Caregiver Strain Index), which will include questions assessing stress and anxiety related to patient's cancer treatment costs as well as prioritization of treatment costs in the list of disease-related concerns.

6.5 Performance Status:

Patients will be graded according to the Zubrod Performance Status Scale.

POINT DESCRIPTION

- 0 Fully active, able to carry on all pre-disease performance without restriction.
- 1 Restricted in physically strenuous activity but ambulatory and able to carry out work of a light or sedentary nature, e.g., light housework, office work.
- Ambulatory and capable of self-care but unable to carry out any work activities; up and about more than 50% of waking hours.
- 3 Capable of limited self-care, confined to bed or chair more than 50% of waking hours.
- 4 Completely disabled; cannot carry on any self-care; totally confined to bed or chair,

